The following patient and surgical risk factors have been shown to contribute to intraoperative critical events: age <1 year, ASA physical status III and IV, urgency of the surgical procedure, and preexisting comorbidities. The level of training of the anaesthesia providers and the number of years of experience, as well as the type of anaesthesia and surgery done are potentially important risk factors. (13)

Study rationale

African Surgical Outcomes Study in Paediatric patients (ASOS-Paeds) determined the incidence of in-hospital postoperative complications up to 30 days after surgery in paediatric surgical patients across different hospitals in Africa. This study will evaluate the intra-operative critical incidents reported in ASOS-Paeds. It is hoped that these findings will contribute to improving perioperative care for paediatric surgical patients in Africa.

Aims and objectives of the “severe critical incidents” analysis

Aims

The aims of this study are to describe the incidence of intraoperative severe critical events, the types of severe critical events, and risk factors independently associated with severe critical events.

Objectives of the study

Primary objective

1. To describe the incidence of intra-operative severe critical events in paediatric surgical patients in Africa

Secondary objectives

1. To describe the categories and types of severe critical events
2. To identify risk factors independently associated with severe critical events

Sensitivity analyses

1. Two sensitivity analyses will be conducted:
 - a. The sensitivity analyses of elective surgical patients, and emergency surgical patients, and
 - b. A sensitivity analysis excluding the two countries providing more than 10% of the patients to the dataset (Egypt and South Africa)

Statistical Analysis Plan

A) Data Validation

- Report on the number of incomplete data points
- Report on primary outcome data
 - % missing data for incidence of severe critical events
- Provide STROBE diagram of recruited patients

B) Statistical tests

- Categorical variables will be described as number and proportions (percentage) and will be compared using appropriate Chi-squared or Fisher's exact tests.
- Continuous variables will be calculated and reported as mean and standard deviation (SD) if normally distributed, or median and inter-quartile range (IQR) if not normally distributed.

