- Comparisons of continuous variables between groups will be performed using t-tests, one-way ANOVA or equivalent non-parametric tests as appropriate.
- If $< 5\%$ of data are missing for the primary outcomes, a complete case analysis will be conducted
- A p-value of less than 0.05 will be considered statistically significant for all analyses
- Generalized mixed effects model analysis will be performed for exploration of candidate variables for prediction of risks for the primary outcome i.e. incidence of severe critical events
 - Further description to follow in the section discussing risk prediction
- Sensitivity analyses will be conducted.

C) Primary objective

1. To describe the incidence of intra-operative severe critical events in paediatric surgical patients in Africa

This will be presented as number (n/N), percentage (%)

The cohort will be described according to the variables (Table 1)

- Age, ASA PS, sex
- Comorbidities
- Describe the Hospital, Surgery and Anaesthesia information
 - Hospital level
 - Urgency of surgery (elective, emergency)
 - Severity of surgery (minor, intermediate, severe),
 - Indication for surgery
 - Type of surgery
 - Intraoperative factors
 - Most senior anaesthetist
 - Most senior surgeon

- Time of induction

D) Secondary objectives

1. To describe the categories and type of intra-operative severe critical events
 - Outcome definitions are defined in the study protocol
 - The categories of severe critical events will be presented as airway, respiratory, cardiovascular, metabolic, and other severe critical events categories (Table 2) using % to indicate the incidence (number of patients with severe critical events divided by the number of patients) and 95% confidence intervals.
 - To describe the types of severe critical events within each category
 - The categories and types of severe critical events will also be presented by the level of facility, and the level of the anesthesia providers (Table S1)
2. To identify risk factors independently associated with severe critical events
 - All variables will be entered into the model, unless there are less than 10 events per variable. If this is the case, risk factors with a p value ≤ 0.05 for severe critical events identified by univariate analysis will be entered into the model. (Table 3) The reference category for the surgical discipline will be decided by the surgical discipline with the lowest incidence of severe critical events

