 - Results will be presented as unadjusted and adjusted odds ratios (ORs) with 95% confidence intervals (CI's).

Analyses will be conducted using Statistical Package for the Social Sciences (SPSS) version 30 (SPSS Inc., Chicago, IL, USA) and R: A language and environment for statistical computing. Vienna, Austria: R Foundation for Statistical Computing (2024) using Studio: Integrated Development Environment for R. Boston, MA: RStudio, Inc. (2024).

Tables

Table 1. Description of cohort including patient, surgical, anaesthesia and facility characteristics

		All patients (n=)	Patients with severe critical events (n=)	Patients without severe critical events (n=)
		n/N (%)	n/N (%)	n/N (%)
Age	Mean (SD) Median (IQR)			
Sex				
Male				
Female				
Age categories				
0-28 days				
29 days to < 1 yr				
1 to < 4 yr				
4 to < 13 yr				
13 to <18 yr				
ASA PS				
I				
II				
III				
IV-V				
Urgency of surgery				
Routine				
Emergency				
Severity of surgery				
Minor				
Intermediate				
Major				
Primary indication for surgery				
Non-communicable disease				
Infective				
Trauma				
Congenital				
Hospital level				
First				
Second				
Third				
Most senior anaesthetist				

Specialist			
Non-specialist physician			
Nurse			
Non-physician			
Most senior surgeon			
Specialist			
Non-specialist physician			
Nurse			
Non-physician			
Type of surgery			
Orthopaedic			
Cardiac			
ENT			
Gynaecological			
Hepatobiliary			
Kidney/urological			
Gastrointestinal			
Thoracic			
Ophthalmology			
Maxillo-facial/ dental			
Plastic/cutaneous			
Neurosurgery			
Burns			
Comorbidities			
Cardiac disease			
Chronic respiratory disease			
Neurological disorder			
HIV/AIDS			
Cancer			
Current respiratory tract infection			
Intraoperative factors			
Duration			
Surgical checklist used			
Time			
Daytime			
After hours			

Table 2: The categories and types of intra-operative severe critical events

	Overall	Incidence
	n/N (%)	% (95% CI)
Categories of anaesthetic severe critical incidents		
Any		
Any Airway/respiratory		
Any CVS		
Any Other		
Types of severe critical events by category		
Airway/respiratory		
Difficult BMV		
Difficult Intubation		
Failed Intubation		
Laryngospasm		
Bronchospasm		
Aspiration		
Severe Hypoxia		
CVS		
Bradycardia		
Cardiovascular instability		
Cardiac Arrest		
Metabolic		
Temp < 36		
Low Glucose		
Other		
Anaphylaxis		
Drug error		
Death		
Yes		
No		

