Table 3. Univariable and multivariable analysis of preoperative factors associated with intra-operative severe critical events

	Univariable		Multivariable	
	OR (95% CI)	p-value	OR (95% CI)	p-value
Age (per 1 year)				
Sex				
Male				
Female	Reference			
ASA PS				
I	Reference			
II				
III				
IV-V				
Urgency of surgery				
Routine	Reference			
Emergency				
Severity of surgery				
Minor	Reference			
Intermediate				
Major				
Primary indication for surgery				
Non-communicable disease	Reference			
Infective				
Trauma				
Congenital				
Hospital level				
First				
Second				
Third	Reference			
Most senior surgeon				
Specialist	Reference			
Non-specialist physician				
Nurse				
Non-physician				
Most senior anaesthetist				
Specialist	Reference			

Non-specialist physician				
Nurse				
Non-physician				
Type of surgery				
Orthopaedic				
Cardiac				
ENT				
Gynaecological				
Hepatobiliary				
Kidney/urological				
Gastrointestinal				
Thoracic				
Ophthalmology				
Maxillo-facial/dental				
Plastic/cutaneous				
Neurosurgery				
Burns				
Comorbidities				
Cardiac disease				
Chronic respiratory disease				
Neurological disorder				
HIV/AIDS				
Cancer				
Current respiratory tract infection				
Intraoperative factors				
Duration				
Surgical checklist used	Reference			
Surgical checklist not used				
Time				
Daytime	Reference			
After hours				

Table S1: Intra-operative severe critical events by facility and anaesthesia provider

	Hospital level			Most senior anaesthetist			
	District	Regional	Tertiary	Specialist	Non-specialist physician	Nurse	Non-physician
Categories of anaesthetic severe critical incidents							
Any							
Any Airway/respiratory							
Any CVS							
Any Other							
Types of severe critical events by category							
Airway/respiratory							
Difficult BMV							
Difficult Intubation							
Failed Intubation							
Laryngospasm							
Bronchospasm							
Aspiration							
Severe Hypoxia							
CVS							
Bradycardia							
Cardiovascular instability							

Cardiac Arrest							
Metabolic							
Temp < 36							
Low Glucose							
Other							
Anaphylaxis							
Drug error							
Death							
Yes							
No							

References

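### Table 3 of the SAP is laid out for level-by-level p-values at 0.05, and no joint test per factor is named for the adjusted model, so the plan does not say how a multi-level factor is judged an independent risk factor

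*SAP*

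**What the plan says.** Secondary objective 2 of the SAP is "To identify risk factors independently associated with severe critical events". SAP section B sets one threshold: "A p-value of less than 0.05 will be considered statistically significant for all analyses". It does not say whether that applies to a factor or to a level.

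The model is described in section B: "Generalized mixed effects model analysis will be performed for exploration of candidate variables for prediction of risks for the primary outcome". Section B promises more detail later, but section D, item 2, adds only three things:

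- An entry rule. All variables enter unless there are fewer than 10 events per variable, in which case "risk factors with a p value ≤ 0.05 for severe critical events identified by univariate analysis will be entered into the model".
- The reference for type of surgery: "The reference category for the surgical discipline will be decided by the surgical discipline with the lowest incidence of severe critical events".
- The reporting format, which is unadjusted and adjusted odds ratios with 95% confidence intervals.

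Table 3, "Univariable and multivariable analysis of preoperative factors associated with intra-operative severe critical events", has an odds ratio column and a p-value column for each analysis. There is one row per level and a marked reference row for each multi-level factor except type of surgery. The factor heading rows are blank.

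On unadjusted comparisons, section B says that categorical variables "will be compared using appropriate Chi-squared or Fisher's exact tests". Neither document names a likelihood-ratio or Wald test of a whole factor in the regression model.

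**The concern.** Objective 2 should end in a list of independent risk factors. A factor with several levels has several p-values in Table 3, each against a reference and each judged at 0.05. The more levels a factor has, the more chances it has of one p-value below 0.05 when nothing is going on. A list built from those p-values has a false-positive rate that varies from factor to factor and is highest for type of surgery. It also depends on which level is the reference, whereas a joint test does not.

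The same gap reaches the entry screen. A multi-level factor has several univariable p-values, and the SAP does not say which of them decides entry.

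**Working it through.** **Inputs from the documents.** Threshold 0.05 (SAP section B; two-sided assumed). N = 7000 (protocol summary; protocol section 5.10 says there is no specific sample size). Event rates 2.32%, 5.2% and 11.7% (SAP introduction, from other studies).

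**Assumed.** The share of patients in each level, which the documents do not give.

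**No plan figure to reproduce.** The documents state no factor-level error rate. As a baseline, a simulated two-level factor gave 4.8% to 5.1%.

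**Step 1: count the contrasts in Table 3.** ASA 3, severity 2, indication 3, hospital level 2, surgeon 3, anaesthetist 3, type of surgery 12. Total 3 + 2 + 3 + 2 + 3 + 3 + 12 = 28 in seven factors.

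**Step 2: rough guide, treating contrasts as independent.** 1 - 0.95^m gives 9.8% for m = 2, 14.3% for m = 3 and 46.0% for m = 12. Contrasts that share a reference are correlated, so a simulation is needed.

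**Step 3: null simulation.** 20,000 runs per setting, the same true event rate in every level, and an unadjusted Wald test of each level against the reference. The entries are the percentage of runs with at least one level at p < 0.05.

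| Factor | Shares | 2.32% | 5.2% | 11.7% |
|---|---|---|---|---|
| 3 levels | equal | 8.8 | 9.2 | 8.9 |
| 3 levels | 6:3:1, large reference | 8.8 | 9.4 | 9.4 |
| 3 levels | 1:3:6, small reference | 7.3 | 7.6 | 7.7 |
| 4 levels | equal | 11.9 | 12.5 | 12.3 |
| 4 levels | 60:25:10:5, large reference | 12.5 | 13.3 | 13.9 |
| 4 levels | 5:10:25:60, small reference | 8.4 | 9.1 | 9.1 |
| 13 levels, fixed reference | equal | 28.5 | 30.6 | 31.0 |
| 13 levels, fixed reference | skewed | 33.1 | 37.1 | 40.1 |
| 13 levels, lowest-incidence reference | equal | 70.3 | 74.4 | 75.4 |
| 13 levels, lowest-incidence reference | skewed | 28.6 | 39.9 | 49.3 |

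The lowest-incidence rows use the lowest non-zero rate. One joint chi-squared test on k - 1 degrees of freedom rejected in 4.5% to 5.3% of runs in every setting. A separate null simulation with a fixed reference gave about 8-10%, 12-15% and 28-40%. The combined ranges are therefore 7-10%, 8-15% and 28-40%.

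**Step 4: all seven factors, if all were null and independent (fixed reference, extremes of the table).**

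- Expected false flags, low end: 0.285 + 4 × 0.084 + 2 × 0.073 = 0.77.
- Expected false flags, high end: 0.401 + 4 × 0.139 + 2 × 0.094 = 1.15.
- With joint tests: 7 × 0.05 = 0.35.
- Chance of at least one, low end: 1 - 0.715 × 0.916^4 × 0.927^2 = 57%.
- Chance of at least one, high end: 1 - 0.599 × 0.861^4 × 0.906^2 = 73%.
- With joint tests: 1 - 0.95^7 = 30%.

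**Step 5: could the entry screen apply?** Table 3 has 19 variables, or 28 + 12 = 40 model terms if age and duration are linear. At 5.2% there are 7000 × 0.052 = 364 events: 364/19 = 19.2 per variable, but 364/40 = 9.1 per term. Whether the 10-event limit is crossed depends on how variables are counted.

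**The case against.** **The any-level rule is not written.** A reader might infer from the layout and the blanket threshold that the SAP declares a factor significant once any one level is below 0.05. No sentence says so, and the blank heading rows of Table 3 could hold a joint p-value. This objection stands. What remains is that no other rule is given and nothing says the heading rows will be used.

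**A joint test is named elsewhere.** A reader might infer that the SAP contains no overall test at all. That is too broad: a chi-squared or Fisher test on a whole categorical variable is a joint test. But it is unadjusted, so it cannot show independent association, and the SAP does not tie it to the entry screen.

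**The inflation is not large everywhere.** This stands. For the six three- and four-level factors the tabulated rates are about 1.5 to 2.8 times nominal (7.3/5 to 13.9/5). Only type of surgery is far off, at about 6 to 8 times with a fixed reference (28.5/5 to 40.1/5).

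**The simulation is not the planned analysis.** It has no covariates and no hospital clustering, so the figures show the order of size and are not predictions. The lowest-incidence reference is usually worse than a fixed one but not always: with skewed shares at 2.32% it gave 28.6% against 33.1%.

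**Level contrasts are proper questions.** Non-physician against specialist, for example, is of interest in itself. Removing level p-values is a presentation choice and is not needed.

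**Conclusion.** The gap is real but limited. For the adjusted model behind secondary objective 2, the SAP names no joint test per factor, and its table shell provides for level p-values at 0.05. If those are used to name risk factors, a null factor is flagged in roughly 7-10% (three levels), 8-15% (four levels) or 28-40% (type of surgery, fixed reference) of studies. Under the SAP's own reference rule the type-of-surgery figure is about 29-75%. A joint test holds about 5%. All of this rests on N = 7000, event rates borrowed from other studies, assumed level shares, and no adjustment or clustering.

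The seven-factor total of about 0.8 to 1.15 false flags against 0.35 should be read only as an illustration. It assumes that every factor is null, while the SAP introduction reports that ASA status and urgency have been shown to contribute.

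A reader might also infer that the main results are in doubt. The documents do not support that: the primary objective is a descriptive incidence, and the model is presented as exploration. The odds ratios and intervals stay as they are, unless the entry screen applies. In that case the choice of p-value could change which factors enter the adjusted model.

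**What to change.** Add one sentence to SAP section D, item 2. For each factor with more than two levels, a single joint likelihood-ratio or Wald p-value from the mixed model decides whether the factor is called an independent risk factor, and the matching univariable joint p-value is used if the entry screen applies. Print these p-values on the factor heading rows of Table 3. State that level odds ratios, intervals and any level p-values are descriptive, or are interpreted only after a significant joint test.

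The joint p-value does not depend on the reference level, so it also protects the call on type of surgery from the data-chosen reference. The individual discipline contrasts would still carry that dependence.

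The cost is a sentence, a small layout change and a routine model comparison. The price is that fewer factors will be called significant, and a 12-degree-of-freedom test has less power when only one discipline differs from the rest.

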Intraoperative critical events can have multiple risk factors and contribute to anaesthesia related complications. The incidence ranges from 2.32% to 11.7% and shows significant variability among different settings. The largest intraoperative critical event study in Europe showed a high number of intraoperative severe critical events (5.2%) with significant variability between hospitals. Respiratory critical events were the most common (3.1%) followed by cardiovascular instability (1.9%). The immediate poor outcome was 5.4%. (6)

There are specific considerations that should be sought in Paediatric population anaesthesia related critical events. These may include the choice of drug and their response. Additionally, the anaesthesia related adverse effects may have long term sequelae for children. As a result, studying those critical events will help to identify the factors related and final outcomes which will help in standardizing the care. It will also be a base to advocate for intraoperative care.

Reported incidences from high income countries

Studies from Europe reported incidences ranging from 0.14% for serious adverse events to 3.4% for critical incidents. (7) Similarly a study done by Cohen et al showed a severe anaesthesia critical event rate of 1.4 per 1000. The commonest events were respiratory followed by cardiac. (8) A large international multicentric cohort study covering North America, Oceania and Europe reported an incidence of 24 % for intraoperative adverse events. (9)

Reported incidences from low- and middle-income countries

The reported incidences for critical events vary across low and middle-income countries (LMICs). A South Korean study reported a 0.4% incidence of paediatric anaesthesia related critical incidents, with respiratory events been the commonest (55% of the cases), (10) compared to an Indian study which reported a 12% incidence, predominated by respiratory complications. (11) Generally, LMICs may carry at least double the burden of intraoperative critical events to high-income countries, although the risk should be similar to that of HICs. These excess events should be preventable. (12)

Types of complications

Respiratory related complications are most commonly reported, followed by cardiovascular events.

Risks associated with complications

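### The fallback for the risk-factor model selects covariates on univariate p ≤ 0.05 alone, and the 10-events rule that triggers it does not say whether it counts 19 factors or 40 coefficients

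*SAP*

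**What the plan says.** SAP section D, item 2, gives the entry rule for the model of severe critical events: "All variables will be entered into the model, unless there are less than 10 events per variable". Where that fails, "risk factors with a p value ≤ 0.05 for severe critical events identified by univariate analysis will be entered into the model". The candidates are the rows of Table 3, titled "Univariable and multivariable analysis of preoperative factors associated with intra-operative severe critical events". The SAP does not say whether a factor with several levels counts once or once per coefficient. It sets no further criterion for the fallback.

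Under its heading on risks, the SAP lists as already shown "age <1 year, ASA physical status III and IV, urgency of the surgical procedure, and preexisting comorbidities". It adds that the anaesthesia provider's training and experience, and the "type of anaesthesia and surgery done are potentially important risk factors".

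Two sets of sensitivity analyses are planned: "The sensitivity analyses of elective surgical patients, and emergency surgical patients", and "A sensitivity analysis excluding the two countries providing more than 10% of the patients to the dataset". Section B says only that they will be done. It does not say whether the Table 3 model is refitted in them.

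Protocol 5.10 fixes no sample size and undertakes to adapt models to the event rate so that logistic models are not overfitted. Protocol 5.11 selects factors on three grounds: univariate p < 0.05, biological plausibility and a low rate of missing data.

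**The concern.** Two things are left open or weakly specified.

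- **The trigger.** Overfitting depends on the number of coefficients estimated, not on the number of row headings in a table. Type of surgery is one factor but takes 12 coefficients. Counted per factor, the rule admits all 40 coefficients from 190 events, which is 190/40 = 4.75 each.
- **The fallback.** A univariate p-value depends on how common a factor is as well as on how strong it is. A real but uncommon risk factor, such as a single comorbidity, can fail the screen. The odds ratios left in the model are then not adjusted for it, although the objective is to find factors independently associated with the outcome. If a weak, uncommon factor does pass, it tends to do so because its estimate came out high.

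**Working it through.** The documents give no expected event count or coefficient count for this model, so there is no stated figure to reproduce.

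**Step 1. Count Table 3** (coefficients = levels − 1). Age 1, sex 1, ASA 3, urgency 1, severity 2, indication 3, hospital level 2, surgeon 3, anaesthetist 3, type of surgery 12, six comorbidities 6, duration 1 (taken as linear), checklist 1, time 1. The sum is 40 coefficients from 10 + 6 + 3 = 19 factors. Random effects are not counted.

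**Step 2. Where the rule switches.** Per factor: 10 × 19 = 190 events. Per coefficient: 10 × 40 = 400 events. With the 7000 patients of the protocol summary, 190/7000 = 2.7% and 400/7000 = 5.7%. The two counts disagree only from 190 to 399 events.

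**Step 3. Full cohort.** Events = 7000 × incidence. The SAP introduction says "The incidence ranges from 2.32% to 11.7" per cent and gives 5.2% for the large European study. The 10.4% row is an assumption: twice 5.2%, following the SAP's remark that low- and middle-income countries may carry at least double the burden.

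| Incidence | Events | Per factor (÷19) | Per coefficient (÷40) | Rule gives |
|---|---|---|---|---|
| 2.32% | 162 | 8.5 | 4.1 | fallback on either count |
| 5.2% | 364 | 19.2 | 9.1 | the counts disagree |
| 10.4% | 728 | 38.3 | 18.2 | full model on either count |
| 11.7% | 819 | 43.1 | 20.5 | full model on either count |

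**Step 4. What the screen does at 162 events.** Simulation: 200,000 cohorts of 7000 at 2.32% incidence for each setting, one binary factor, Wald test of the log odds ratio at two-sided 0.05. Prevalences and odds ratios are assumed.

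| Prevalence | True OR 1.5: kept | Median OR if kept | True OR 2.0: kept | Median OR if kept |
|---|---|---|---|---|
| 5% | 28% | 2.0 | 66% | 2.2 |
| 10% | 42% | 1.8 | 87% | 2.1 |
| 20% | 60% | 1.6 | 97% | 2.0 |
| 40% | 72% | 1.6 | 99% | 2.0 |

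Loss and exaggeration therefore concern rarer or weaker factors. Common factors with a clear effect nearly always pass. The simulation is univariable and ignores clustering; no multivariable or mixed model was simulated.

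**Step 5. The fallback need not cure the shortage that triggers it.** If only type of surgery, ASA and anaesthetist pass, the model has 12 + 3 + 3 = 18 coefficients, and 162/18 = 9.0 events each. Nothing in the rule requires a second check.

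**Step 6. Sensitivity analyses, only if the model is refitted there and incidence is constant.**

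- Country exclusion: two countries with more than 10% each leave less than 80% of patients. At 5.2% that is at most 0.8 × 364 = 291 events, or 15.3 per factor and 7.3 per coefficient. At 10.4% it is at most 582, or 14.6 per coefficient.
- Urgency strata (18 factors and 39 coefficients without urgency; a half share is assumed): 182 events at 5.2%, or 10.1 per factor and 4.7 per coefficient; 364 at 10.4%, or 20.2 and 9.3.

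**The case against.** - **The counting issue is an ambiguity, not an error.** If *variable* means coefficient, the rule already does what is asked, and one line of definition settles it. This stands. In the full cohort the choice matters only at 190 to 399 events, and at the 5.2% benchmark the shortfall is 9.1 against 10, which is marginal.
- **The screening loss is narrow.** On the per-factor count and 7000 patients, the full cohort reaches the fallback only below 2.7% incidence. Even there an odds ratio of 2.0 is kept in 87% or more of samples once prevalence is 10%. This limits the size of the problem. It does not justify a selection rule that ignores what the SAP says is known.
- **Protocol 5.11 already supplies plausibility and missing-data criteria.** Those were written for the models of postoperative complications, critical care admission and death, so they do not strictly govern this outcome. The SAP's fallback does not carry them over, and an analyst following it would use p alone. Bringing the two documents into line is part of the repair.
- **The model is exploratory and secondary.** SAP section B describes it as exploring candidate predictors. That lowers the priority, but the stated objective is still independent association, which depends on which covariates are adjusted for.

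A reader might infer that the main exposure lies in the sensitivity analyses, because subsets always hold fewer events. The documents do not support that. The SAP does not say that the model is refitted there, so these analyses could concern incidence alone. At 5.2% the full cohort is itself already in the range where the two counts disagree.

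**Conclusion.** The point holds, with the weight on the fallback. Selection on univariate p ≤ 0.05 alone uses no subject-matter criterion, is not re-checked against 10 events per variable, and can discard rarer factors that the SAP names as shown risks. The undefined count is a lesser matter: it moves the switch between 190 and 400 events and decides the model at the 5.2% benchmark, but with little overfitting at stake there. It would be wrong to conclude that the planned full-cohort model is badly overfitted: at 10.4% or more it is adequate on either count.

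Only the secondary risk-factor objective is affected, not the primary incidence. The figures rest on 7000 patients, on incidences taken or derived from the SAP's introduction, and on assumed prevalences, odds ratios and stratum shares. The actual event count is not in the documents, so which branch of the rule will apply is unknown. The change should be made, but the trial's main result does not depend on it.

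**What to change.** 1. Define the rule as 10 events per estimated fixed-effect coefficient, keeping the SAP's own figure.
2. Replace the univariate fallback with a covariate set fixed in advance on subject-matter grounds, in line with protocol 5.11. Always keep age, ASA, urgency, the six comorbidities and most senior anaesthetist: 1 + 3 + 1 + 6 + 3 = 14 coefficients, needing 140 events. At 162 events that is 162/14 = 11.6 each.
3. Add the remaining factors as far as events allow, in an order fixed blind to outcome, merging sparse surgery types blind to outcome if needed. At 364 events, 36 coefficients fit (364/36 = 10.1). The order and the grouping are for the sponsor to choose.
4. State whether the model is refitted in the sensitivity analyses. If so, use the same covariate set, without urgency in the urgency strata.
5. Report events per coefficient for every model and state the limit where it is below 10. Two cases are foreseeable: the core itself falls short below 140/7000 = 2.0% incidence, and a half-share urgency stratum at 2.32% has 81/13 = 6.2.
6. Keep the univariable odds ratios for all factors in Table 3.

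The cost is a few sentences of SAP text, with no new data and the same mixed model. The downside is that, with few events, lower-ranked factors get no adjusted odds ratio and surgery types may be coarser.

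### Table 3 adjusts the six comorbidities for ASA grade, so their adjusted odds ratios can fall to 1 or below, and the only other estimate planned is unadjusted

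*SAP*

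**What the plan says.** The SAP's second secondary objective is "To identify risk factors independently associated with severe critical events". Its introduction (Risks associated with complications) lists as known risk factors "age <1 year, ASA physical status III and IV, urgency of the surgical procedure, and preexisting comorbidities". ASA PS and comorbidities thus appear side by side, with nothing on how one relates to the other.

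Section D, item 2 gives the entry rule: "All variables will be entered into the model, unless there are less than 10 events per variable". If that threshold is missed, "risk factors with a p value ≤ 0.05 for severe critical events identified by univariate analysis will be entered into the model". Table 3 lists ASA PS (I as reference, II, III, IV-V) and cardiac disease, chronic respiratory disease, neurological disorder, HIV/AIDS, cancer and current respiratory tract infection under the same univariable and multivariable columns. Unadjusted and adjusted ORs are both reported.

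The two sensitivity analyses are elective and emergency subsets, and exclusion of two countries. Neither omits ASA PS. The SAP does not say how an ASA-adjusted comorbidity OR is to be read.

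**The concern.** ASA PS is a summary grade that reflects, among other things, the diseases listed further down the same table. Holding it fixed has two separate effects on a comorbidity's OR.

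- Any risk that the disease expresses through its grade is removed. What remains is the association beyond grade. That is a legitimate quantity, but not the same as asking whether children with the disease are at higher risk after allowing for age, urgency and type of surgery.
- If unlisted disease or acute illness raises both the grade and the risk of an event, comparison within a grade is distorted. A child graded III for a listed disease is compared with children graded III for something else, possibly worse. This can push the OR below the disease's own direct effect, and below 1 when that effect is absent.

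At stake is the list of independent risk factors that objective 2 will produce. The unadjusted column does not fill the gap, because it is not adjusted for age, urgency, type of surgery or anything else in Table 3. No planned estimate lies between the crude OR and the ASA-conditioned one.

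**Working it through.** The documents give no OR, power or overlap figure on this point, so there is nothing to reproduce.

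**Step 1: do ASA PS and the comorbidities really enter together?** Table 3 has 19 variables, or 40 coefficients: age 1, sex 1, ASA 3, urgency 1, severity 2, indication 3, hospital level 2, surgeon 3, anaesthetist 3, type of surgery 12, comorbidities 6, duration 1, checklist 1, time 1. With the 7000 patients in the Protocol summary (Protocol 5.10 says there is no specific sample size) and the incidences in the SAP introduction, events = 7000 × incidence:

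| Incidence | Events | Events ÷ 19 variables | Events ÷ 40 coefficients |
|---|---|---|---|
| 2.32% | 162 | 8.5 | 4.1 |
| 5.2% | 364 | 19.2 | 9.1 |
| 11.7% | 819 | 43.1 | 20.5 |

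So the rule that applies depends on the incidence and on what counts as a variable. Under full entry all six comorbidities are adjusted for ASA PS. Under the fallback, any comorbidity that passes the univariate screen is adjusted for ASA PS if ASA PS also passes. Neither rule separates them.

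**Step 2: how far can the OR move?** A simulation used N = 7000, 5.2% events and 300 data sets per scenario. All other inputs are assumptions. One comorbidity C has prevalence 3% or 8%. A latent score a·C + u·U + logistic noise is cut into four ASA grades (0 to 3), where U is unmeasured severity. The log-odds of an event are m + b·grade + ln(direct OR)·C + u·U. A logistic model for C was fitted with and without ASA. Significant means p < 0.05 with OR above 1, two-sided testing assumed. Paired figures are for 3% / 8% prevalence.

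| Scenario | OR without ASA | OR with ASA | Significant without ASA | Significant with ASA |
|---|---|---|---|---|
| C unrelated to ASA; direct OR 2 (a=0, b=0.7, u=0) | 1.91 / 1.93 | 1.93 / 1.98 | 73% / 96% | 73% / 96% |
| Mostly direct, OR 2 (a=2, b=0.2, u=0) | 2.34 / 2.43 | 1.94 / 2.03 | 91% / 100% | 74% / 98% |
| Part through ASA, direct OR 1.5 (a=2, b=0.45, u=0) | 2.26 / 2.27 | 1.47 / 1.48 | 88% / 100% | 39% / 64% |
| Wholly through ASA (a=2, b=0.7, u=0) | 1.95 / 1.95 | 0.97 / 1.01 | 68% / 97% | 3% / 3% |
| Same, plus unmeasured severity (u=0.8) | 1.85 / 1.81 | 0.78 / 0.76 | 65% / 89% | 0% / 0% |

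**Step 3: what causes the change?** It is not loss of precision. Standard errors rose only from 0.247 to 0.252 (2%) at the least and from 0.150 to 0.163 (9%) at the most. With u = 0 the ASA-adjusted OR recovers the direct effect (1.47 against 1.5; 0.97 to 1.01 against 1), so there the model answers a different question correctly. In the last row the direct effect is still 1 but the estimate is 0.76 to 0.78, and that is bias.

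**Step 4: could a neutral comorbidity look protective?** In the last row, z = ln(0.76)/0.176 = −1.56 at 8% prevalence and ln(0.78)/0.265 = −0.94 at 3%. The chance of a significant protective result is roughly Φ(−1.96 + 1.56) = Φ(−0.40), about 34%, and Φ(−1.96 + 0.94) = Φ(−1.02), about 15%. A second simulation (7000 children, about 5-6% events, other inputs again assumed) moved a true direct OR of 2 from 1.99 to 1.24, with significance falling from 89% to 18% of data sets. It gave a comorbidity with no effect an ASA-adjusted OR of 0.59, significant in 49%.

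**The case against.** The strongest case for the plan is that the model does what the objective asks. Whether a comorbidity adds information beyond ASA grade is a fair meaning of independent association. The SAP (B) also describes the model as "exploration of candidate variables for prediction of risks for the primary outcome", and overlapping predictors are no fault in prediction. This stands in part. However, the SAP text plans no discrimination, calibration or validation; its output is individual ORs, which will be read one by one. Step 3 also shows that with unmeasured severity the estimate is biased even for the beyond-ASA question.

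Three stronger readings are tempting, and the documents support none of them.

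- A reader might infer that the adjusted ORs must shrink for all six comorbidities. The documents do not say how ASA was graded or how closely it follows each disease. The first row of the simulation shows no loss.
- A reader might infer that a comorbidity would be reported as not associated at all. The unadjusted OR stands beside the adjusted one, so the crude association stays visible. What can be lost is the label of independent association.
- A reader might infer that the ASA-free OR is the right one. It is less adjusted for unlisted disease and acute state, and it still conditions on severity of surgery, duration, checklist use and the other Table 3 factors. It is not a total effect.

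It is also fair to say that the simulations leave out the other Table 3 terms and the random effects. They show a mechanism and a range, not the loss to expect in this study.

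**Conclusion.** The point holds in conditional form. The SAP adjusts the comorbidities for ASA PS, plans no model without it, and gives no rule for interpretation. Under the assumed inputs, adding ASA moved a comorbidity OR of about 2 to anywhere from 0.76 to no change, and the share of data sets showing a significant increase in risk fell by anything from nothing to almost all. Where each of the six falls in that range cannot be told from the documents, which is why both estimates should be shown.

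The conclusion rests on ASA PS being graded partly from systemic disease (general clinical knowledge) and on assumed prevalences, effect sizes and strength of link. A larger sample would not cure it, because the change lies in what is estimated. It bears on a secondary objective only; the incidence estimate is unaffected.

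**What to change.** Add a column to Table 3, or a third sensitivity analysis, with the same mixed model without ASA PS. Keep the same patients, the same random effects and the same other covariates (including any chosen by the fallback screen), so that the two columns differ only by ASA PS. Then:

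- show both adjusted ORs with 95% confidence intervals side by side;
- state that the ASA-adjusted comorbidity OR means association beyond ASA grade;
- state that no comorbidity will be called not independently associated, or protective, from the ASA-adjusted estimate alone;
- state the limits of the ASA-free ORs (less adjustment for unlisted disease and acute state, still conditional on the other Table 3 factors), so that neither column is the sole basis for interpretation.

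The cost is one extra fit, one extra column and a few sentences. No new data are needed.
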